The 12 adapted modules are presented in **Table 1**. In the study, these modules will be delivered to the participants on paper in the T2D-appropriate food boxes and in easy to access online versions, which link to the videos summarizing the key concepts and demonstrating cooking techniques. All materials are translated into English, Spanish, and Marshallese.

2. Design T2D-appropriate food boxes. The project team led by an endocrinologist, registered nurse, and registered dietitian designed 12 weekly food boxes to be home delivered to each participant. The boxes were adapted from the American Diabetes Association Create Your Plate method,⁴⁹ which emphasizes non-starchy vegetables, proteins, and grains, consistent with the meal pattern promoted in the ACP DSME.⁴⁸ In addition, the boxes will include food that largely reflects Feeding America's Foods to Encourage framework,⁵⁰ which was developed by nutrition experts and food bank leaders to meet USDA dietary guidelines⁵¹ and MyPlate framework.⁵²

The boxes will include ~9,000 calories of food, equivalent to the amount the average household would receive *pro-rated per week* from an average Arkansas food pantry.³⁷ Each box will include fresh fruits and vegetables, as well as the ingredients necessary to prepare the recipes included with that week's DSME curriculum. If a certain item is unavailable or out of stock, there is a list of potential substitutions that are of equal nutritional content compared to the first choice food item. Each week's box will include an educational fact sheet of the week's DSME module, including links and QR codes leading to the videos. Links to the week's online materials, which present the same content as the paper materials, will be texted or emailed to each participant based on their preferred contact method on the day each box is delivered. **Table 2** shows an example T2D-appropriate food box.

3. Recruit and enroll up to 110 participants. Study participants may be

recruited from waiting areas of food pantries located in Benton and Washington Counties in northwest Arkansas. (See Letters of Support from local food pantries.) Due to social distancing and public health guidelines related to COVID-19 each of the food pantries have established drive-thru clinics where participants can remain isolated in their vehicles while completing data collection. Participants may use these drive-thru clinics for consent and all biometric collection.

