4. Collect data. For each participant, participation will take place over 22 weeks (Weeks 1-4: Pre-intervention data collection; Weeks 5-16: Intervention; Weeks 17-22: Post-intervention data collection). **Table 3** describes the study measures and outcomes. Data collection will take place at pre-intervention and post-intervention for each participant. At enrollment (i.e., pre-intervention) and one week after the 12th food box delivery (i.e. post-intervention), participants will provide data on glycemic control (measured by HbA1c), physical activity, body mass index (BMI), T2D self-management behaviors, T2D knowledge, T2D self-efficacy, and food security. To enhance the study's significance in characterizing the diet patterns and fruit and vegetable consumption of low-income food insecure people with T2D, we are collecting extensive diet quality data measures pre-intervention and post-intervention. Specifically, we will collect 24-hour dietary recalls. Participants will be asked to document their dietary intake over a 24-hour period three times within four weeks. Two of the dietary recalls must be collected from a weekday and one of the recalls must be collected from a weekend day. Also, Skin carotenoid level will be measured using a Veggie Meter® optical skin scanner, which uses Raman Spectroscopy. The Veggie Meter assesses frequency changes in reflected light to calculate carotenoid presence. Skin carotenoid levels are a biomarker of fruit and vegetable dietary

Title: Delivering Health: An Integrated Approach to Address Diabetes in the Context of Food Insecurity

PI: [name]

intake. Participants will be asked to complete a survey via (email, text or in person) asking about their preference for the food provided in the food boxes.

Initial data collection will take place in a private space immediately following enrollment. The remaining pre-intervention data collection and post-intervention data collections will take place via telephone and at locations of each participant's choosing (e.g., HbA1c will be collected at home or at a community-based location such as a food pantry). Our team has necessary expertise and equipment to complete data collection in homes or community-based locations, having successfully completed thousands of such data collection events.^{37,43,54-61}

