The study has a single-arm, pre-post study design. All participants will receive the intervention (i.e., 12 weekly food boxes including the adapted DSME materials). Our target sample size for recruitment is 100. Assuming a repeated measures t-test, two-sided $\alpha=.05$, and a Pearson correlation between repeated measures of $r=.5$, we will have 80% power to detect a Cohen's d effect size of 0.28. For context, Chrvala, Sherr, & Lipman's (2016) meta-analysis found that on average DSME led to a 0.6% improvement in HbA1c.²⁵ Assuming a standard deviation of 1.5%, this translates to Cohen's d of 0.4 (i.e., $0.6/1.5=0.4$). Thus, the proposed intervention with a sample size of 100 is powered to detect a small-to-medium effect consistent with the expected effect size for standard DSME interventions in the context of research trials, and smaller than the effect found in previous food pantry-based DSME interventions.^{33,34}

Table 3. Delivering Health study measures and outcomes	
Variables	Instrument(s) or Measure(s)
COVARIATES	
Demographic & Socioeconomic	Demographic (age, gender, marital status, race, number of adults and children in the household) and socioeconomic (education, employment status, insurance coverage, WIC and SNAP benefits) variables will be captured using validated questions from the Behavior Risk Factor Surveillance System (BRFSS) ⁶² and National Health Interview Study (NHIS). ¹²⁰
EFFECTIVENESS OUTCOMES	
HbA1c	Finger stick blood collection will be used to test HbA1c using a Siemens DCA Vantage analyzer that can be taken into the field. ⁶³
Diet Quality and Fruit and Vegetable Consumption	Skin carotenoid level will be measured using a Veggie Meter® optical skin scanner, which uses Raman Spectroscopy. The Veggie Meter assesses frequency changes in reflected light to calculate carotenoid presence. 24-hour dietary recalls will be collected using the widely-used Nutrition Data System for Research (NDSR) software, which includes over 18,000 foods. ⁶⁴ NDSR will be used to calculate Healthy Eating Index-2015 (HEI) scores and fruit and vegetable consumption. HEI-2015 scores comprise nine

Title: Delivering Health: An Integrated Approach to Address Diabetes in the Context of Food Insecurity

PI: [name]

	component scores (e.g., vegetables, dairy) and are recommended by National Cancer Institute to assess impact of diet quality interventions. ^{65,66}

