Table 4. DSME and T2D-appropriate Food Boxes Intervention

Evidence-based DSME Curriculum	■ Consistent with the American Association of Diabetes Educators, the adapted ACP DSME will cover the topics of understanding diabetes, eating right, being active, checking blood sugar, taking medicines, keeping feet healthy, and insulin. The adapted curriculum consists of 12 modules, which will include recipes and information on cooking and shopping when on a limited income and with foods commonly found at food pantries.
T2D-appropriate food boxes	■ Each weekly food box will include ~9,000 calories of food, equivalent to the amount the average household receives prorated per week from an average Arkansas food pantry. ³⁷ The boxes will follow the American Diabetes Association Create Your Plate method, consistent with the ACP DSME. Food will be purchased from a local grocery store.
Intervention Delivery	■ Food boxes will be delivered to participants' homes once per week. Each week's box will include a two-page educational fact sheet version of the week's DSME module, including links and QR codes leading to videos supporting the week's curriculum module. Links to the week's online materials, which present the same content as the paper materials, will be texted or emailed to each participant the day their box is delivered.
Dosage	■ 12 food boxes (including curriculum) delivered once per week over 12 weeks

Given the study's longitudinal design, participant retention will be crucial. We engaged stakeholders to develop a retention plan. The plan specifies that study staff responsible for recruitment and retention will be bilingual (Spanish/English or Marshallese/English). Study staff will obtain each participant's contact information and preferred method of contact. Before each follow-up data collection visit or call, research staff will contact participants about the upcoming data collection.

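### Does the unstated start of the post-intervention recall window leave the HEI primary outcome undefined?

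*Combined protocol and SAP*

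**What the plan says.** Item 4 (Collect data) sets the calendar: "Weeks 5-16: Intervention; Weeks 17-22: Post-intervention data collection", preceded by four weeks of pre-intervention collection. It places a list of measures, including HbA1c, BMI and food security, at enrollment and at "one week after the 12th food box delivery (i.e. post-intervention"). That list does not name the dietary recalls.

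The next sentence introduces the diet measures: "we are collecting extensive diet quality data measures pre-intervention and post-intervention". The recall rule follows: "Participants will be asked to document their dietary intake over a 24-hour period three times within four weeks", and "Two of the dietary recalls must be collected from a weekday and one of the recalls must be collected from a weekend day". No sentence gives the first day of the post-intervention four weeks.

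The Data Analysis section makes HEI one of two primary outcomes and compares pre with post. On design, item 4 says: "The study has a single-arm, pre-post study design". Table 4 gives the dosage as "12 food boxes (including curriculum) delivered once per week over 12 weeks".

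**The concern.** The intervention is largely food, and HEI scores what was eaten. Item 2 sizes each box as a weekly amount: "The boxes will include ~9,000 calories of food, equivalent to the amount the average household would receive" from a pantry, prorated to a week. A recall made a few days after box 12 may therefore record box food, while one made five or six weeks later is less likely to.

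The pre-intervention phase lasts four weeks, the same as the recall span, so its position is fixed. The post-intervention phase lasts six weeks, so a four-week span can float within it. Four weeks is also only a maximum, so the three recalls could cluster at either end. All pre-intervention recalls come before box 1, so any mixing of early and late recalls affects only the post side of the change.

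What seems to be at stake is the meaning of a primary outcome: diet just after the last box, or diet up to about six weeks later, with a lag that can differ between participants.

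**Working it through.** **Inputs.** From item 4: pre-intervention Weeks 1-4, intervention Weeks 5-16, post-intervention Weeks 17-22; three recalls within four weeks. From Table 4: 12 weekly boxes. From the compensation paragraph after Table 4: $10 per recall, $60 in total. The delivery day within Week 16 is not stated; call it d, from 1 to 7.

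**The plan's own figures.** 4 + 12 + 6 = 22 weeks, as stated. $60 / $10 = 6 recalls, that is, three before and three after. Box k falls in Week 4 + k, so box 12 falls in Week 16.

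**Outer window.** Count box 12 as day 0. Week 17 opens at day 8 - d and Week 22 ends at day 49 - d. The length is (49 - d) - (8 - d) + 1 = 42 days for every d.

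**Recalls in the week box 12 supplies.** Take this as days 1 to 6, before a thirteenth box would have been due. The phase contains 6 - (8 - d) + 1 = d - 1 of those days. If recalls are spread evenly over Weeks 17-20 (28 days), the expected share is (d - 1)/28.

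| d | Phase, days after box 12 | Phase days within days 1-6 | Even-spread share |
|---|---|---|---|
| 1 | 7-48 | 0 | 0/28 = 0% |
| 4 | 4-45 | 3 | 3/28 = 10.7% |
| 7 | 1-42 | 6 | 6/28 = 21.4% |

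The range of days 1 to 48 is thus an envelope over delivery days, and no single participant has it. All three recalls can fall in days 1-6 only if at least three such days exist, that is, only for d of 4 or more. A full four-week span can start no later than day 49 - d - 27 = 22 - d, which is day 21 for d = 1 and day 15 for d = 7.

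**Natural reading.** Item 4 attaches the label post-intervention to the point a week after box 12, then uses the same label for the diet data. If the four weeks open at that point, they cover days 7 to 7 + 27 = 34. This fits inside Weeks 17-22 for every d, since 8 - d is at most 7 and 49 - d is at least 42. The calendar is consistent with this reading: for d = 1, a week after box 12 is exactly the first day of Week 17, and no recall can then fall in days 1-6.

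**How sharp the six-day boundary is.** The example box in Table 2 holds canned fruit, vegetables, beans, chicken and tuna, instant rice, frozen spinach and olive oil. Much of it keeps beyond a week. The shares above assume no carry-over, so they overstate the contrast between early and late recalls.

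**The case for a change.** The strongest case for a change runs as follows. The sentence that fixes the one-week point does not list the recalls, and three recalls on separate days cannot share one time point. The day 7 to 34 window is therefore an inference. Even with delivery on the first day of Week 16, a lag of 7 to 48 days remains possible. The lag could also distort the exploratory dosage models in the Data Analysis section if participants who are hard to reach both receive fewer boxes and are called later. Stating the start would take one sentence.

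Some of this stands. The start of the span is not written down, and the lag may vary between participants. The link between late calls and missed boxes is plausible, but nothing in the documents supports it, and it concerns an exploratory analysis.

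The rest is weaker. A single point can open a window: enrollment is also a single point labelled pre-intervention, and its recalls run over the four weeks of the pre-intervention phase. The single-arm design does not aggravate the matter either. A control group without boxes would leave the variation in time since box 12 in the treated arm, and that variation would pass into the difference between arms. A hard closing date would also have a price, because it would discard late recalls that the six-week phase now accepts and add missing data on a primary outcome.

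**Conclusion.** No change follows. The plan bounds the post-intervention recalls twice, by Weeks 17-22 and by the four-week span, and its own use of the term post-intervention points to about days 7 to 34 after box 12. Followed as written, it gives a valid comparison of diet quality before the programme with diet quality in the weeks after deliveries end.

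On the loosest reading, the lag lies within a 42-day phase per participant, and the even-spread share of recalls in the first six days is 0% to 21%. The upper figure needs delivery on the last day of Week 16 and no carry-over of a largely shelf-stable box. Any shift in HEI points is unknown, because the documents give neither an HEI effect nor a standard deviation.

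Analysts can settle the remaining detail when they report. The weekday and weekend rule already requires each recall's date to be known. The delivery date should be known too, since the online links go out on the day each box arrives. If both dates are kept, which I assume, the lag can be tabulated and the HEI result described as diet quality over that period.

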BMI	Weight and height will be used to compute a continuous measure of BMI using the Quetelet Index (kg/m ²). Weight will be measured in light clothing to the nearest 0.5 lb. (0.2 kg) using a calibrated digital scale. Height (without shoes) will be measured to the nearest 0.5 in. using a stadiometer.
Medical Conditions	BRFFS self-report items will assess lifetime prevalence of medical conditions. ⁶²
T2D Self-Management Behaviors	The Summary of Diabetes Self-Care Activities (SDSCA) will be used to measure self-care activities. The SDSCA consists of 12 items to assess the frequency of performing diabetes self-care tasks. ⁶⁷ SDSCA was validated in minority populations, including the Marshallese. ⁶⁸
Oral Health	Oral health will be assessed by a single-item taken from the BRFFS survey. ⁶²
T2D Self-Efficacy	Self-efficacy for health behaviors will be assessed through the Diabetes Management Self-Efficacy Scale (DMSES), which assesses the extent to which respondents are confident in managing their blood sugar, diet, and exercise. ⁶⁹ DMSES was validated in several studies of minority populations, including the Marshallese. ⁶⁸
T2D-related Distress	Psychological distress related to type-2 diabetes will be assessed through PAID-5 scale of the Diabetes Attitudes, Wishes, and Needs second study questionnaire (DAWN2) ¹²²
Food Security	Food security will be assessed using the adapted 10-item USDA screener. ¹²¹
Food Pantry Utilization	Food pantry utilization will be assessed through modified items from Feeding America's Hunger in America Client Survey ¹²³
Medication Adherence	Measures of diabetes medication adherence will be collected with measures from BRFFS ⁶² , NHIS ¹²⁰ , and ARMS-D. ¹²⁴
Cooking Skills and Knowledge	Assessment of participants confidence in following a simple recipe and cooking from basic ingredients will be assessed using items developed for use in low socioeconomic populations. ¹²⁵
PROCESS EVALUATION MEASURES	
Process Indicators	Process evaluation will include tracking indicators of retention (e.g., numbers of participants enrolled, data collection events completed) and dosage (e.g., food boxes successfully received). Post-intervention data collection will include open-ended questions about satisfaction with food boxes and suggestions to improve intervention.

5. Implement intervention. **Table 4** summarizes the intervention.

Title: Delivering Health: An Integrated Approach to Address Diabetes in the Context of Food Insecurity

PI: [name]

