"Participants will be offered a \$40 gift card for participation in each of the two data collection events for a total of \$80. Those participants who only participate in the survey or biometric data collection will receive \$20 for their time. Participants will also be offered \$10 gift cards at each of the dietary recall phone interviews for a total of \$60. Participants will only receive gift cards for the data collection events they complete. If a participant drops out, the study team will document who dropped out and why the drop out occurred. Participants will be able to choose a Tango electronic gift card at each of the data collection events.

Study Population

Up to 110 study participants will be recruited from food pantries located in Benton and Washington Counties in northwest Arkansas.

Inclusion Criteria

- 18 years of age or older
- Food insecure (confirmed with adapted 10-item screener)
- HbA1c levels of ≥ 7

Title: Delivering Health: An Integrated Approach to Address Diabetes in the Context of Food Insecurity

PI: [name]

Exclusion Criteria

- Conditions making it unlikely the participant will be able to follow the protocol, such as terminal illness, non-ambulatory, severe mental illness, severely impaired vision or hearing, eating disorder, or plans to move out of the geographic region
- Pregnant
- Only one adult per household will be enrolled

Risks and Benefits

A risk to study participants is the potential for loss of confidentiality of study data. Measures to protect the confidentiality of study data will be implemented as described in the Data Handling and Recordkeeping section below.

A finger stick is required to collect a small amount of blood for testing, this may cause some discomfort.

The food box deliveries will be packaged to hold the correct temperature of perishable foods for three hours. After that time, or if the box is in any way damaged there is a risk of potentially eating spoiled foods from the food box delivery. There is also a risk of consuming a food item that the participant is unknowingly allergic to. We will do our best to ensure the integrity of the food box deliveries and are always available to contact with any questions regarding the food items in the deliveries.

Potential benefits include provision of nutritionally balanced food to participant's home for the 12 week period of the study. Participants may experience improved health status, specifically related to type 2 diabetes.

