In addition to the potential of benefits to the participants, knowledge gained from the study could potentially benefit patients in the future.

Data Handling and Recordkeeping

The Principal Investigator will carefully monitor study procedures to protect the safety of research subjects, the quality of the data and the integrity of the study.

All study subject material will be assigned a unique identifying code or number. The key to the code will be stored in a secure location in the Office of Community Health and Research. Only the principal investigator and the study coordinator will have access to the code and information that identifies the subject in this study. During data collection events survey data will be collected on a UAMS iPad or laptop using REDCap mobile app (with built in encryption technology). As soon as the data collectors return to UAMS, they will upload the data to the REDCap instance housed on a secure UAMS server and delete the data from the iPad or laptop. Blood specimens collected for HbA1c testing are only used for point of care testing, they will be discarded immediately after the test is performed. At the conclusion of the study the key to the code will be shredded, the data will be permanently de-identified.

Title: Delivering Health: An Integrated Approach to Address Diabetes in the Context of Food Insecurity

PI: [name]

The study will comply with UAMS Admin Guide Policy 3.2.01 – research data, reports and analyses be retained for seven years after final reporting or publication of a project, or longer if required by a sponsor or regulation.

Data Analysis

Analyses will be performed with SAS 9.4. Data will be examined for distributional normality and outliers prior to analyses. Descriptive statistics will be generated for all variables of interest. We will examine patterns and predictors of missing values. If the percentage of missing values is larger than approximately 10%, we will compare models using multiple imputation with those using complete case analysis to examine the potential impact of missing values on the results.

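### The protocol names spoiled food and unrecognised allergy as risks of the boxes but describes no question or record for either, so an absence of reports could not be read as an absence of harm

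*Combined protocol and SAP*

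**What the plan says.** Risks and Benefits (combined protocol and SAP) says that if a delivery passes its three-hour temperature limit or is damaged, "there is a risk of potentially eating spoiled foods from the food box delivery". It adds: "There is also a risk of consuming a food item that the participant is unknowingly allergic to". The response given is best efforts on box integrity, and that staff "are always available to contact with any questions regarding the food items in the deliveries".

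Data Handling and Recordkeeping contains the safety statement: "The Principal Investigator will carefully monitor study procedures to protect the safety of research subjects". It attaches no event definition, form, schedule or review.

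The measures closest to the subject are these:

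- Table 3, Medical Conditions: "BRFFS self-report items will assess lifetime prevalence of medical conditions".
- Table 3, Process Indicators: counts of retention and boxes received, and then "Post-intervention data collection will include open-ended questions about satisfaction with food boxes and suggestions to improve intervention".
- Collect data (project activity 4): a survey by email, text or in person "asking about their preference for the food provided in the food boxes", with no timing given.
- The compensation and dropout paragraph that follows Table 4: "If a participant drops out, the study team will document who dropped out and why the drop out occurred".

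Scheduled data collection is before and after the intervention. The Data Analysis section covers HbA1c, diet quality, covariates, dosage and missing data. It mentions no summary of harms.

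**The concern.** The intervention puts 12 weekly boxes that include perishable food into the homes of people with type 2 diabetes. The protocol recognises that this can go wrong in two specific ways and makes the investigator responsible for safety. Yet no described measure would tell the investigator, or a later reader, whether it did go wrong.

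This is more than missing detail in the write-up. If the information is not asked for while participants are in contact, the analysts cannot recover it afterwards. The trial could then report how many boxes arrived and how well they were liked. If asked whether the boxes made anyone ill, it could say only that nobody had mentioned it. That matters to anyone deciding whether to copy a home-delivery model.

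**Working it through.** **The plan's own figure.** The plan gives no figure for harms. Its only sample-size statement is under Study Design and Procedures: 100 participants, paired test, two-sided alpha 0.05, correlation 0.5, 80% power for d = 0.28. With r = 0.5 the standardised paired difference is 0.28/√(2 × (1 − 0.5)) = 0.28, and n = ((1.960 + 0.842)/0.28)² = 100.1. Exact noncentral-t power at 100 is 79.2%. The statement reproduces. It is used here only as the source of N = 100.

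**Each route set against the two named harms**

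| Route | What it asks | What it could miss |
|---|---|---|
| Contact with staff | Nothing; the participant must start it, and it is framed as questions on food items | Any case not volunteered |
| Dropout reason | Why the person left | Harms that did not lead to leaving |
| Food-preference survey | Liking for the food | Any case not volunteered |
| Open-ended post-intervention questions | Satisfaction and suggestions | Any case not volunteered, and people who do not return |
| Medical Conditions item | Lifetime history | A new, short illness after a box |
| Box tracking | Whether boxes were received | Illness or reaction; condition on arrival is not listed |

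No row is described as asking about illness, reaction or spoiled food. The post-intervention contact falls one week after box 12. For a problem with box 1 that is at least 11 + 1 = 12 weeks of recall.

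**What zero reports would mean.** Let N be the number of participants, p the true proportion harmed and s the fraction of harmed participants whose case reaches the study. Treat participants as independent. The documents give no value for s; the values below are assumptions chosen to show the range.

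With no reports, the one-sided 95% upper limit on p × s is 1 − 0.05^(1/N), so the limit on p is that figure divided by s.

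- N = 100, s = 1: 1 − 0.05^(1/100) = 2.95%. At the maximum enrolment of 110 it is 2.69%.
- N = 100, s = 0.50: 2.95%/0.50 = 5.9%.
- N = 100, s = 0.25: 2.95%/0.25 = 11.8%.

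Conversely, the chance of no report at all is (1 − p × s)^100:

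| True p | s = 1 | s = 0.50 | s = 0.25 |
|---|---|---|---|
| 2% | 13.3% | 36.6% | 60.6% |
| 5% | 0.6% | 8.0% | 28.4% |

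If everyone is asked and answers accurately, silence argues strongly against a 5% harm rate. If a quarter of cases come through, silence would occur more than one time in four at that rate. Since s is unknown, no single limit can be stated.

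**The case against.** The strongest reply is that this is a small effectiveness study of ordinary groceries. It makes no safety claim, and harms do have ways to surface. Ethical Considerations also commits the study to applicable regulations, institutional policy and IRB approval, which may carry event-reporting duties that are not visible here. The survey wording is not in the supplied text and the consent pages were removed.

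Much of that stands, and it limits what can be said. Four stronger readings are tempting, and the documents do not support them.

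- *Harm reaches the study only if a participant calls.* The dropout record, the preference survey and the open-ended questions are other routes.
- *Participants are never asked about harm.* Without the instruments this cannot be shown. What can be shown is that the protocol describes no such question.
- *The first structured contact is 12 weeks after box 1.* The preference survey has no stated timing and could fall during deliveries.
- *One bad item would strike several homes in the same week, or dropouts are the likeliest to have been harmed.* Neither has a source. Enrolment is expected to run from Year 2 Quarter 3 to Year 4 Quarter 2, about 8 quarters or 104 weeks. If it is even, 100 × 12 = 1,200 boxes over 104 weeks is about 11.5 a week, or roughly one home per box number. Batched enrolment or shared items could change this, but the documents describe neither. The protocol also ties spoilage to the delivery and allergy to the individual.

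What the reply does not answer is how cases would be found. Reporting duties apply to events that are known, and none of the described routes asks.

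**Conclusion.** The point holds in limited form. The protocol names two harms of the boxes and a duty to protect safety, and describes no question, record or summary linking them. Cases would surface only if volunteered, so an absence of reports could be neither read as an absence of harm nor converted to a rate.

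The 2.95% limit rests on N = 100, independent participants and full capture. The 5.9% and 11.8% figures rest on assumed capture fractions. They illustrate the problem and are not estimates for this trial. The conclusion does not depend on which fraction is chosen, only on its being unknown. Nothing here suggests that the boxes are unsafe, or that the primary analyses of HbA1c and diet quality are affected.

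**What to change.** Add fixed closed items to Table 3, asked of each enrolled participant at post-intervention and whenever a dropout is documented:

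- *Did any box arrive damaged or warm? (Y/N; which box)*
- *Did you have any illness or allergic reaction that you link to food from a box? (Y/N; which box and item)*

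Address the items to the enrolled participant rather than the household, so that the count matches its denominator. Record the answers in REDCap, pass any positive answer to the investigator, and state in Data Analysis that the count will be reported with the number asked.

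Optionally, add one line to the text or email already sent with each weekly box, inviting the participant to report a problem with the last one. This would shorten the delay, but someone must handle the replies. Those reports remain volunteered and should be shown separately from the closed items.

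The cost is a short item in English, Spanish and Marshallese, a REDCap field and an IRB amendment; no extra visit is needed. Some recall error will remain for early boxes, and people lost without contact will still be missed, which is why the number asked must be reported. With a single arm there is no comparator for background illness, so the result would be a count of illness that participants attribute to the boxes, not an estimate of illness caused by them.
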